procedure (surgical/non-surgical) to the subset containing patients with complete data in those variables for both treatment groups separately. Impute the missing entries of the incomplete data sets $m = 25$ times as follows: Draw a set of regression coefficient from their sampling distribution obtained from fitting the respective linear models outlined above (a different distribution for the regression coefficients will be obtained in the different treatment groups). With these sampled coefficients calculate the predicted blood loss values for the procedures with missing blood loss using the covariate information. To these predicted blood loss values add the realizations of a normally distributed random variable with zero mean and standard deviation equal to the residual standard deviation from the linear model fitted to the complete data set. The random seeds for these 25 imputations will be (11468, 11469, 11470, ..., 11492). On the imputed datasets calculate the blood loss on a patient level.

3. Analysis: Analyze each of the m complete data sets with a t-test or the Mann-Whitney test according to the test result in step 1. This step results in m estimates of the effect and m estimates of the standard deviation.
4. Pooling: Integrate the m analysis results into a final result with the SAS procedure PROC MIANALYZE according to Rubin's combination rules for multiple imputation to obtain the final estimates of mean and variance [28].

For the additional analysis of blood loss which treats the whole eschar removal process as one continuous procedure (see section 7.3.2.2) the multiple imputation will be performed on a patient level. The procedure can be described as follows:

1. Test for normality: The Shapiro-Wilk test will be performed on the dataset of non-missing values in each treatment group. The result of these tests will determine the type of the analysis on the imputed data sets (step 3.). If the normal distribution hypothesis is not rejected at the 5% significance level in either group, then differences in distribution between NexoBrid and SOC will be tested using a t-test. If the normal distribution hypothesis is rejected either in the NexoBrid group or in the SOC group, then the differences in distribution between the treatment groups will be tested using a Mann-Whitney test.

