10.1.2.2. Safety Endpoint: Cosmesis and function at 12 months from wound closure

A higher ratio of missing values is expected in the case of later MVSS values, especially for 24 months. It is expected that the 1 months MVSS value exists. If this is not the case the missing MVSS value will be replaced by the mean MVSS value of all patients who belong to the same treatment group and the same stratum (see Section 11.1.10) at that time point. For missing MVSS values at later time points (3, 6, 12, 18 and 24 months) the following imputation method will be used:

For each time point (1, 3, 6 and 12 months) and each treatment arm separately, a linear regression model with target variable MVSS at 12 months and explanatory variables MVSS at the respective time point and all stratification variables (see Section 11.1.10) is fitted to the data of patients having both MVSS values. Missing MVSS values at 12 months are then

imputed with the prediction of the linear regression model, which has the last non-missing MVSS value before the 12 months measurement for the individual as explanatory variable (i.e. for patients who have the 6 months MVSS measurement but not the 12 months measurement, the 12 months measurement is imputed from the 6 months measurements; for those who have the 3 months measurement but not the 6 months or 12 months measurement the 12 months measurement is imputed from the 3 months measurement; and for those who have the MVSS measurement at 1 month but not at 3 months, 6 months or 12 months the 12 months measurement will be imputed from the 1 month measurement). To this prediction, the realization of a normally distributed random variable with zero mean and standard deviation equal to the residual standard deviation from the linear model is added. The random seed for this imputation is 45318.

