Similarly, for each time point (1, 3, 6, 12 and 18 months) and each treatment arm separately, a linear regression model with target variable MVSS at 24 months and explanatory variables MVSS at the respective time point and all stratification variables (see Section 11.1.10) is fitted to the data of patients having both MVSS values. Missing MVSS values at 24 months are then imputed with the prediction of the linear regression model, which has the last non-missing MVSS value before the 24 months measurement for the individual as explanatory variable. To this prediction, the realization of a normally distributed random variable with zero mean and standard deviation equal to the residual standard deviation from the linear model is added. The random seed for this imputation is 45448.

Using this imputation method deviates from the handling of missing data specified in the protocol. There, simple LOCF was intended. However, LOCF is not considered a suitable imputation method for the MVSS values as early MVSS values are not considered representative for late MVSS measurements in the same individual. Furthermore, LOCF is heavily criticized in the statistics community since it may lead to biased results even when the missing occurs completely at random (see [29], [30]).

Additionally, best case – worst case imputations will be used as a supporting sensitivity analysis. One using the worst case MVSS value of 9 (observed maximum MVSS value in the SOC group in the previous study MW2004-11-02) for all missing MVSS data and one using the best case value of 0 (observed minimum MVSS value in the SOC group in the previous study MW2004-11-02).

10.1.2.3. *Safety Endpoint: Cosmesis and function at 24 months from wound closure*

See 10.1.2.2.

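### Missing 12- and 24-month MVSS scores are imputed once and analysed as observed, so the 95% CI compared with 1.9 is too narrow (modestly so at 10% missing or less)

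*SAP*

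**What the plan says.** Section 10.1.2.2 covers missing MVSS at both 12 and 24 months. In each arm, the final score is regressed on an earlier MVSS and the stratification variables. A missing 12-month score is predicted from the model "which has the last non-missing MVSS value before the 12 months measurement for the individual as explanatory variable"; the 24-month rule is the same, using the model "which has the last non-missing MVSS value before the 24 months measurement for the individual as explanatory variable". Then: "To this prediction, the realization of a normally distributed random variable with zero mean and standard deviation equal to the residual standard deviation" of that model is added. One seed is given for each time point: "The random seed for this imputation is 45318" and, for 24 months, "The random seed for this imputation is 45448". No number of imputations, coefficient draw or pooling step appears.

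Sections 11.2.4.2 and 11.3.4.3 refer to 10.1.2.2 for missing data. They fit a linear model with treatment, depth, TBSA and number of target wounds, and reject the null hypothesis of a difference of 1.9 or more if the upper 95% limit is below 1.9.

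The SAP also says: "A higher ratio of missing values is expected in the case of later MVSS values, especially for 24 months". Its MVSS sensitivity analyses put in either "the worst case MVSS value of 9 (observed maximum MVSS value in the SOC group in the previous study MW2004-11-02) for all missing" MVSS data, or 0.

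For blood loss (section 10.1.1.3) the instruction differs: "Draw a set of regression coefficient from their sampling distribution obtained from fitting the respective linear models outlined above". This is done 25 times and the results are pooled with PROC MIANALYZE.

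**The concern.** A single stochastic fill leaves the reported standard error close to its complete-data value. The true variance of the treatment coefficient rises for two reasons: fewer real scores inform it, and the random residuals add noise of their own. An ordinary linear model run on the completed data sees neither.

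The direction of the error is known. An interval that is too narrow makes it easier to conclude that NexoBrid is not worse by more than 1.9 units. This matters for results near the margin and grows with the amount of missing data, which the SAP expects to be greatest at 24 months. Section 6.4 has the 12- and 24-month MVSS analyses programmed twice, independently, so the results are evidently meant to be relied on. Linking the rejection rule to the cosmesis and function part of the third objective (section 2.2) is an inference; the SAP does not state it.

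**Working it through.** **Inputs from the SAP.** 75 patients each in the NexoBrid and SOC arms (9.3.1); margin 1.9 and the upper 95% limit rule (11.2.4.2, 11.3.4.3), which is a one-sided 2.5% test; stratification by 2 TBSA levels, 3 depth levels and 5 center groups (11.1.10).

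**Assumed, because the SAP gives no values.** SD σ = 2; a share f missing completely at random, equal in both arms; correlation ρ between last observed and final score of 0.3 to 0.8, the high end suiting month 6 or month 18 as last score; strata shares. There is no MVSS power or precision figure in the SAP to reproduce.

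**Closed form.** With complete data the variance of the difference is 2σ²/n, so SE = √(2 × 4 / 75) = 0.327. Regression imputation multiplies the variance by 1 + (1−ρ²)·f/(1−f), and the single residual draw adds (1−ρ²)·f. Hence

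true variance ≈ (2σ²/n) × [1 + (1−ρ²)(f/(1−f) + f)],

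while the model still reports about 2σ²/n. The one-sided error at a true difference of 1.9 is Φ(−1.96/√[bracket]), which does not depend on σ. Example with f = 0.2 and ρ = 0.3: 0.91 × (0.25 + 0.20) = 0.4095; √1.4095 = 1.187; 1.96/1.187 = 1.651; error 4.9%.

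**Simulation.** The arm-specific fill (last MVSS plus TBSA, depth and center-group dummies, fixed coefficients, one residual draw) was followed by the section 11.2.4.2 model. Each cell from 10% to 40% missing had 26,000 trials (16,000 at 0% and 5%). Ranges run from ρ = 0.8 to ρ = 0.3.

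| Missing | Error, closed form | Error, simulated | Reported SE | True SD |
|---|---|---|---|---|
| 0% | 2.5% | 2.6% | 0.33-0.34 | – |
| 5% | – | 2.7-3.0% | 0.33-0.34 | – |
| 10% | 2.9-3.6% | 2.8-3.7% | 0.33-0.34 | 0.35-0.37 |
| 20% | 3.5-4.9% | 3.5-4.8% | 0.33-0.34 | 0.36-0.40 |
| 30% | 4.1-6.4% | 3.9-6.3% | 0.33-0.34 | 0.38-0.44 |
| 40% | 4.8-8.1% | 5.0-8.2% | 0.33-0.34 | 0.40-0.48 |

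A second simulation, with ρ from 0.3 to 0.7 and 1,500 trials per cell, gave two-sided coverage of 92.5-93.5% at 10% missing, 90.2-92.8% at 20% and 83.1-87.3% at 40%.

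**After the change.** With 25 imputations, drawn coefficients, residual SD held fixed as in the blood-loss text, and Rubin's rules, the error was 2.0-3.1% in every cell from 10% to 40% missing (4,000 trials per cell). Drawing the residual SD as well gave 1.9-2.5%.

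**Do the 9 and 0 fills cover the gap?** They too are single fills, with the same value in both arms. With equal missing shares they multiply the difference by (1−f): at f = 0.2, a true 1.9 becomes 0.8 × 1.9 = 1.52. The 9 fill also widens the interval. With mean 3 and SD 2 the filled variance is 0.8 × 4 + 0.2 × 0.8 × 6² = 8.96, so SE = √(2 × 8.96 / 75) = 0.49 (simulated 0.45-0.51). At 20% missing, ρ = 0.6 and equal missing shares, pass rates for main / 9 fill / 0 fill were 74.0 / 70.5 / 88.1% at a difference of 1.0 and 4.4 / 4.9 / 9.0% at 1.9. So the 9 fill can be stricter or laxer than the main analysis, and neither fill repairs the standard error.

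**The case against.** The strongest reply concerns weight. Section 11 makes stage 1 the only inductive analysis, the hierarchy in 11.1.8 leaves MVSS out, and 11.2.8 and 11.3.8 call stage 2 and 3 testing exploratory. No sample size rests on MVSS. This stands and keeps the point from being graver. It does not remove it: an exploratory label excuses the lack of multiplicity control, but not an interval that is called 95% and covers less.

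Every input to the size is assumed, and at 10% missing or less the excess error is small. That is correct; the larger figures need 20% missing or more.

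Decisions seldom change if the arms are similar. That also stands. At 20% missing and no true difference, single and multiple imputation both declare non-inferiority in at least 99.8% of trials.

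Blood loss is a secondary efficacy endpoint in the hierarchy, so fuller treatment there is not in itself inconsistent, and the SAP did improve on the protocol's LOCF. Both are fair. The comparison shows mainly that the remedy is already written.

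The 9 and 0 fill pass rates hold only for equal missing numbers per arm. With random numbers, the 9 fill at 20% missing passes about 12.6% at a difference of 1.9 and 65% at 1.0. Those pass rates should be read as illustration only; the finding that the fills do not reliably cover the gap is unaffected.

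Fixed seeds rule out choosing a favourable draw. True, but the verdict can still hang on the draw: at 20% missing and a true difference of 1.0, two seeds on the same data disagreed in 9-14% of trials.

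**Conclusion.** The concern holds: the procedure is wrong as written and should be corrected before the stage 2 analysis. The interval is too narrow in the direction that favours non-inferiority. The true SD exceeds the reported SE slightly at 10% missing and substantially at 30-40%, and the one-sided error goes from just above nominal to two or three times nominal over that range. The direction follows from the procedure itself. The size rests on the assumed missing rate, correlation and missing-completely-at-random mechanism; the error rates do not depend on the assumed SD. Replacing a missing month-1 score by a stratum mean (also in 10.1.2.2) was not simulated.

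**What to change.** In section 10.1.2.2, impute missing 12-month and 24-month MVSS by arm, 25 times, drawing the regression coefficients for each imputation and listing 25 seeds per time point. Fit the 11.2.4.2 (or 11.3.4.3) model to each completed data set, pool the treatment coefficient and its standard error with PROC MIANALYZE, and compare the pooled upper 95% limit with 1.9. Keep the 9 and 0 fills as supporting analyses. Optional refinements: draw the residual SD too, bring a missing month-1 score into the same procedure, and add a tipping-point analysis shifting imputed NexoBrid scores upward, as section 10.1.1 does for the primary endpoint.

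The work is SAP wording and some programming. The interval widens: SE 0.34-0.36 at 10% missing, 0.35-0.38 at 20%, 0.37-0.41 at 30% and 0.39-0.46 at 40%, instead of 0.33-0.34. Non-inferiority declared, single against multiple imputation:

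| True difference | 20% missing | 40% missing |
|---|---|---|
| 0 | at least 99.8% with either | 99.3-99.9% v 98.3-99.9% |
| 0.5 | 96.8-98.0% v 95.4-97.8% | 93.0-96.9% v 84.9-93.6% |
| 1.0 | 73.2-74.1% v 65.7-71.0% | 68.8-72.5% v 47.8-62.4% |

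Little is lost if the arms are truly similar. The loss is real at a difference of 1.0 with heavy missingness, where it reflects uncertainty that the current interval hides.

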10.3.4.2. Safety Endpoint: Cosmesis and function at 12 months from wound closure

MVSS sub scores at 12 months for pigmentation, pliability, height, vascularity, pain and pruritus will be added up to obtain the overall MVSS score (range 0 to 18) at 12 months per target wound. The patient MVSS score will be the average of the MVSS over all TWs. Additionally, the average MVSS score for donor site scars will be calculated per patient.

10.3.4.3. *Safety Endpoint: Cosmesis and function at 24 months from wound closure*

MVSS sub scores at 24 months for pigmentation, pliability, height, vascularity, pain and pruritus will be added up to obtain the overall MVSS score (range 0 to 18) at 24 months per target wound. The patient MVSS score will be the average of the MVSS over all TWs. Additionally, the average MVSS score for donor site scars will be calculated per patient.

10.3.4.4. *General Parameters of safety*

Volume of blood transfusions given

The volume of blood transfusions given during hospitalization will be computed for each patient as $V_{WB} + \frac{5}{3}V_{PC}$, where V_{WB} and V_{PC} are the volume (in milliliters) of whole blood and packed red blood cells transfused. As in the calculation of blood loss in Section 10.3.3.3.1, the factor of 5/3 is derived from chapter 5 of Transfusion Medicine, 4th Edition [31] and compensates for the fact that equal volumes of whole blood and packed red blood cells are not comparable.

The volume of blood transfused will be calculated overall, as well as separately for volumes transfused before start of treatment, during the ER period, within 1 week after the ER period and later than 1 week after the ER period for each patient.

Extent of analgesia, anesthesia and antibiotic use

The numbers and percentages of patients per each level of sedation (see definitions in Appendix 13.1.2) per procedure (in topical arms: 1st and second topical application, surgical rescue procedures and non-surgical rescue procedures; in SOC arms: surgical procedures and non-surgical procedures) will be calculated.

The number of days of exposure to antibiotic drugs will be calculated for each patient. This will be done overall, for antibiotic use due to AE involvement (as indicated in the eCRF) and for prophylactic antibiotic use (as indicated in the eCRF) separately.

Incidence of increased interstitial/compartment syndrome

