11.2.4.2. Safety Endpoint: Cosmesis and function at 12 months from wound closure

The MVSS score for a patient will be calculated as described in Section 10.3.4.2. The mean and standard error of this MVSS score (for the target wounds) at 12 months will be estimated for each treatment group and presented as shown in Table 4. The treatment groups will be compared using a linear model with MVSS score as the dependent variable. The explanatory variables in the model will include treatment, and the following variables: overall TW depth (all TWs full thickness, mixed TWs, all TWs deep partial thickness), “Total %TBSA per patient” and number of TWs (1, 2, ≥ 3). The coefficient corresponding to the treatment group will be estimated and will represent the estimated mean difference in MVSS score between NexoBrid and SOC adjusted for any imbalance in the stratification factors. The results of the regression analysis will be presented as in Table 7.

A clinically meaningful difference will be incorporated into the analysis that will represent a 1.9 or more units advantage to the SOC group, so that the analysis will show whether the NexoBrid group is estimated to have on average a MVSS score that is not worse by more than 1.9 units than the score for the SOC group. That is, the following hypothesis are about to be tested:

$$H_0: \Delta \geq 1.9 \quad vs. \quad H_1: \Delta < 1.9$$

Where Δ is the mean difference in MVSS score between NexoBrid and SOC adjusted for any imbalance in the stratification factors. These hypotheses will be tested by comparing the 95% confidence interval for the coefficient of the treatment group from the linear model outlined above to the clinically meaningful difference 1.9. The null hypothesis will be rejected if the upper bound of this interval is smaller than 1.9.

For handling of missing data see Section 10.1.2.2.

11.2.4.3. *Safety Endpoint: Cosmesis and function at 24 months from wound closure*

Not applicable for this stage of analysis since the relevant information for all patients is not available yet. This endpoint will be analyzed in the third stage analysis (see 11.3.4.3).

11.2.4.4. *Adverse Events*

In this analysis, only the adverse events occurring after the 3 months follow up and until the 12 months follow up (including AEs from the first stage that are still ongoing) will be analyzed.

All adverse events will be listed (see Table 14).

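### The MVSS missing-data sensitivity runs give both arms the same value, so none tests the case that threatens non-inferiority: missing NexoBrid scars worse than missing SOC scars

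*SAP*

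**What the plan says.** The main MVSS analysis imputes missing 12- and 24-month scores by a linear regression fitted within each arm, using the last available score and the stratification factors (SAP section 10.1.2.2). The same section warns: "A higher ratio of missing values is expected in the case of later MVSS values, especially for 24 months". It then adds that best-case and worst-case "imputations will be used as a supporting sensitivity analysis". The first run is described as "One using the worst case MVSS value of 9", a number that the SAP takes from the highest SOC score in its earlier trial MW2004-11-02. The fill is applied "for all missing MVSS data and one using the best case value of 0", the latter being the lowest SOC score in that trial. Neither run is split by arm.

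Sections 11.2.4.2 and 11.3.4.3 test whether NexoBrid is worse than SOC by 1.9 units or more, by "comparing the 95% confidence interval for the coefficient of the treatment group" with that margin: "The null hypothesis will be rejected if the upper bound of this interval is smaller than 1.9". Neither section adds a further missing-data sensitivity analysis.

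For the primary endpoint, section 10.1.1 also plans two common-value runs. It adds a third analysis, a tipping point that lowers the assumed success probability of missing NexoBrid patients only.

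**The concern.** Filling both arms with one constant tends to make the arms look alike. In a superiority test that is cautious. In a test against an upper margin it can favour the conclusion being sought.

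The regression imputation assumes that missing patients resemble observed patients of the same arm with similar earlier scores. A sensitivity analysis should challenge that assumption in the direction that would overturn non-inferiority, namely missing NexoBrid scars being worse. Objective 3 of the SAP includes showing no unacceptable harm on long-term cosmesis and function. A robustness check on that claim should be able to fail for that reason, above all at the visits where the plan expects most missing data.

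**Working it through.** **Inputs from the SAP.** Fill values 9 and 0 (10.1.2.2); margin 1.9 and upper 95% bound, so one-sided 2.5% (11.2.4.2, 11.3.4.3); 75 patients per arm (9.3.1). The stated range, "overall MVSS score (range 0 to 18) at 12 months per target wound", reproduces from the item maxima in Table 2: 3 + 3 + 5 + 3 + 2 + 2 = 18.

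**Assumptions, because the SAP gives no MVSS mean, SD or missing rate.** SOC mean 3.5; SD 2, 2.5 or 3; 10, 20 or 30% missing, completely at random.

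**Step 1: expected difference.** With fractions mN and mS missing, arm means μN and μS, and common fill v:

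D = (1 − mN)μN − (1 − mS)μS + v(mN − mS)

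If mN = mS = m, the last term vanishes and D = (1 − m)Δ, whatever v, the mean or the SD. For Δ = 1.9: 0.9 × 1.9 = 1.71; 0.8 × 1.9 = 1.52; 0.7 × 1.9 = 1.33.

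**Step 2: chance of declaring non-inferiority when the truth is 1.9.** The variance in an arm is (1 − m)SD² + m(1 − m)(v − μ)². SE² is the sum over both arms divided by 75, and the chance of passing is Φ((1.9 − D)/SE − 1.96).

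Example with m = 0.2, v = 9, SD 2.5:
- NexoBrid (mean 5.4): 0.8 × 6.25 + 0.16 × 3.6² = 7.07
- SOC (mean 3.5): 0.8 × 6.25 + 0.16 × 5.5² = 9.84
- SE = √(16.91/75) = 0.475
- Φ(0.38/0.475 − 1.96) = Φ(−1.16) = 12.3%

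| Missing in each arm | D | Fill 9, SD 2 / 2.5 / 3 | Fill 0, SD 2 / 2.5 / 3 |
|---|---|---|---|
| 10% | 1.71 | 7.1 / 6.2 / 5.6% | 7.2 / 6.2 / 5.6% |
| 20% | 1.52 | 14.5 / 12.3 / 10.6% | 14.7 / 12.4 / 10.7% |
| 30% | 1.33 | 25.1 / 21.5 / 18.4% | 25.6 / 21.8 / 18.7% |

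The reference value is 2.5%. A simulation at SD 2.5 gave about 6, 12 and 21% for both fills.

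**Step 3: where the pattern does not hold (SD 2.5).**
- *True difference 0, equal missingness.* The run with 9 passes in 98.1 / 96.0 / 94.4% at 10 / 20 / 30% missing. Observed cases alone pass in 99.3 / 98.6 / 97.3%, and full data in 99.6%. The imputed 9s widen the interval, so passing is harder.
- *25% missing on NexoBrid, 15% on SOC, true difference 0.5.* Fill 9: D = 0.75 × 4.0 − 0.85 × 3.5 + 9 × 0.10 = 0.925, passing in 50% against 86.5% for observed cases. Fill 0: D = 3.000 − 2.975 = 0.025. The two runs move in opposite directions.

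**Step 4: what neither run varies.** D in either run depends on the observed scores and on how many values are missing in each arm. It does not depend on how bad the missing NexoBrid scars are relative to the missing SOC scars. If missing NexoBrid scars were worse than imputed by δ, the difference would rise by mN × δ, for example 0.2 units per unit of δ at 20% missing. No planned run shows this.

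**The case against.** The other side has several fair points.

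- A reader might infer that these runs always make non-inferiority easier, and more so as data go missing. Step 3 shows otherwise: the claim needs similar missingness in both arms and a NexoBrid arm that is truly worse. The runs do react to unequal drop-out.
- A reader might infer that the error lies in choosing 9 on a scale that ends at 18. The SAP says openly where 9 comes from, and a patient's score is an average over target wounds, so 18 would require the maximum on every item in every wound. Nor would 18 in both arms cure the dilution: D is still (1 − m)Δ.
- A reader might ask for the opposite extremes, NexoBrid 9 and SOC 0. With no true difference and 20% missing, that fill alone gives 9 × 0.2 = 1.8 and passes only about 4% of the time. A bound that fails almost automatically says little.
- The runs are only supportive. The main analysis imputes within arm, and sections 11.2.8 and 11.3.8 label testing at stages 2 and 3 exploratory. The Table 4 layout shows missing counts by arm, so an imbalance would be visible.

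All of this stands and limits the point. It does not supply the missing test: no planned run shifts the missing NexoBrid scores alone.

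**Conclusion.** The concern holds in a limited form. The only missing-data sensitivity runs for the MVSS non-inferiority comparisons use one value for both arms, and none sets missing NexoBrid scars worse than missing SOC scars.

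Under equal, completely random missingness the shrinkage by (1 − m) is exact and needs no assumption about mean, SD or fill value. The rates of roughly 6, 12 and 21% at the margin are illustrations that rest on the assumed mean, SD, missing rates and full enrolment of 75 per arm.

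The documents do not support reading this as an inflated error rate for the trial's MVSS conclusion. The rates describe supporting runs, and the main analysis is a different one. The weakness is that passing both runs would not show that non-inferiority is robust to the missing data.

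**What to change.** Add a delta-adjusted tipping-point analysis to section 10.1.2.2 for both 12 and 24 months, in the spirit of section 10.1.1:

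1. Take the arm-specific regression imputation as already specified, with the same seeds, so that runs differ only in the shift.
2. Add 0, 0.5, 1.0, ... MVSS units to the imputed values of NexoBrid patients only; leave SOC unchanged.
3. Refit the linear model of 11.2.4.2 or 11.3.4.3 each time, and report the shift at which the upper 95% bound reaches 1.9, with the number of imputed values per arm.

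The runs with 9 and 0 can remain as descriptive support, with a sentence saying that they are not bounds for the non-inferiority conclusion. Changing 9 to 18, or adding an opposite-extremes run, is not needed.

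The cost is a few lines of SAP text and one small extra analysis at stages 2 and 3. The sensitivity results may look less favourable.
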